### **7.3 Prohibited Concomitant Medications, Therapies, and Foods**

#### **7.3.1 Prohibited Concomitant Medications**

The concomitant use of the following medications will be prohibited during the treatment period out of concern for the effects on safety, PK, and pharmacodynamics.

Furthermore, in Part A, the prohibited concomitant medications may not be used until the end of the post-treatment observation period.

- GnRH agonists
- GnRH antagonists
- Steroidal antiandrogens
- Nonsteroidal antiandrogens
- Drugs that include corticosteroids (except for topical drugs)
- Male sex hormone preparations
- Female sex hormone preparations
- 5 $\alpha$  reductase inhibitors
- Docetaxel
- Other chemotherapy drugs indicated for prostate cancer
- Drugs with moderately powerful to strongly powerful CYP3A4 inhibitory or inducing effects
- Drugs with P-gp inhibitory effects

#### **7.3.2 Prohibited Concomitant Therapies**

The following therapies for prostate cancer will be prohibited from study treatment initiation until the end of safety follow-up.

- Surgical castration
- Prostatectomy
- High-intensity focused ultrasound therapy
- Radiotherapy

### 7.3.3 Food

From study treatment initiation and during the treatment period (in Part A, until the end of the post-treatment observation period), the use of nutritional supplements and the consumption of grapefruit and related beverages/foods will be prohibited unless judged necessary by the investigator.

## 7.4 Subject Management

### 1. Inpatient/outpatient status

Subjects will be admitted to the investigational site from one day before treatment initiation in each cohort (Day -1) until Day 15 in Part A. As a rule, from Day 16 on, the study will be conducted on an outpatient basis until the safety follow-up. However, from Day 27 on, if a subject lives far from the hospital and it would be difficult for the subject to come to the hospital at the scheduled times, or if the subject desires admission, the study may be conducted on an inpatient basis from Day 27 until Day 35 at the latest. While subjects are inpatients in Part A, they will eat meals (breakfast, lunch, and dinner) at specified times. After being discharged as well, subjects will be instructed to avoid eating or drinking excessively until the end of safety follow-up. When subjects are coming in for visits on an outpatient basis, they will be instructed to be sure to eat dinner on the day before the day of a visit at which a blood sample will be collected for laboratory testing, and they will be instructed to return to the hospital on the following day without eating for blood collection and testing, after which they will receive TAK-385 and then eat breakfast at least 30 minutes later.

If a subject desires to return home temporarily during the inpatient period, and it would not interfere with study treatment, observations, or tests, then the investigator may allow the subject to return home temporarily, after carefully checking to be sure that the subject's condition is stable, on the basis of the data that have been collected during the study to that point.

Unless there is a special reason, Part B will as a rule be conducted on an outpatient basis. Subjects will be instructed to observe the scheduled visit times and undergo the examinations and the specified tests. Subjects will also be instructed to inform the investigator promptly if they are not able to come in for a scheduled visit.

### 2. Study treatment

Investigators will instruct subjects to take the study drug 30 minutes before breakfast on each day, and to make sure that the time they take the study drug is the same on each day, to the extent possible.

If a subject forgets to take the study drug 30 minutes before breakfast, the subject should take the drug 30 minutes before lunch on the same day. If a subject forgets to take the study drug both 30 minutes before breakfast and 30 minutes before lunch, the subject should take the study drug 30 minutes before dinner on the same day. It will be explained to subjects that they should not take any study drug that they have forgotten to take on a later day together with the study drug for that day. Subjects will

also be instructed to be sure to note in the patient diary the time they took the study drug as well as whether or not they took the study drug 30 minutes before breakfast.

On scheduled outpatient visit days, subjects will be asked to come to the investigational site in the morning without taking the study drug, and the scheduled tests will be performed.

3. Drinks, etc.

On days on which study drug is to be taken, subjects will be prohibited from drinking anything from 1 hour before dosing until 30 minutes after, other than one cup of water when they take the study drug.

4. Other

Investigators will instruct subjects that, if a subjective symptom emerges, it should be reported, along with the date of onset, severity, outcome, and date of outcome, when the subject next visits the investigational site.

Investigators will instruct subjects not to take any drugs, including over-the-counter drugs, other than the drugs that they are instructed to take, without consulting the investigator in advance.

Subjects will be instructed that, if they are treated at another medical institution in the time between the treatment period and the safety follow-up, they are to report the background for and nature of said treatment to the investigator, and to inform the medical institution in question that they are participating in a clinical study.

## 7.5 Criteria for Discontinuation or Withdrawal of a Subject

Investigators will enter into the electronic case report form (eCRF) the primary reason for discontinuation or withdrawal of the subject from the study, classified into one of the following categories. See Section 9.1.23 for subjects discontinuing before the study treatment initiation (in the case of Part A) or before randomization (in the case of Part B).

### 1. Pretreatment event or adverse event

This will be considered the primary reason if the subject has experienced a PTE or AE that requires early termination because continued participation imposes an unacceptable risk to the subject's health or the subject is unwilling to continue because of the PTE or AE; if a serious AE occurs, the subject temporarily stops taking the study drug, and the AE recurs following study treatment resumption, or does not resolve event after 2 weeks of treatment interruption; or if toxicity that is considered DLT occurs in Part A.

- Liver function test abnormalities

If a LFT abnormality meeting any of the following criteria occurs during study treatment, study drug administration will be discontinued immediately, and appropriate follow-up tests will be performed until the subject's clinical laboratory profile returns to normal, to the level of the first test value obtained after informed

consent (in the case of a PTE), or to baseline (in the case of an AE) (see Section 9.1.8).

- ALT or AST > 3 × ULN; AND total bilirubin > 2 × ULN or PT-INR > 1.5

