Cohort 4 will be conducted after tolerability is confirmed in Cohort 2. Cohort 4 will be conducted for the purpose of evaluating the tolerability of 360 mg as loading dose in Japanese. 360 mg has been found tolerable in single dosing in the overseas phase 1 single-/multiple-dose study (TAK-385\_C27001) [REDACTED].

[figure not shown]
In Part B, subjects will be randomized to receive study drug (TAK-385 loading dose of 320 mg and maintenance dose of either 80 mg or 120 mg – equal numbers of subjects will be randomized to 80 mg and 120 mg) once a day orally to evaluate safety. In addition to the safety assessments, efficacy assessments will also be performed according

to the study schedule, and study drug will be administered until the discontinuation criteria (Section 7.5) are met for each individual subject. After completing 48 weeks of treatment, subjects may, at the discretion of the investigator, and depending on the wished of the subject, continue receiving study drug (for a maximum of 96 weeks), or they may complete the study and be switched to a GnRH agonist (eg, leuprorelin) or a GnHR antagonist (eg, degarelix), starting from the day after the day of the last dose of TAK-385. Subjects withdrawing from the study will not be replaced.

If no problems with tolerability are found in the additional cohort in Part A, then the study will proceed to Part B with a 40 mg group instead of a 120 mg group (TAK-385 loading dose of 320 mg and maintenance dose of 40 mg).

All subjects who receive study drug, whether in Part A or Part B, will undergo safety follow-up 30 to 40 days after the last dose of TAK-385.

[figure not shown]
Part A (Dose-rising phase)

\*1: If tolerability is not confirmed in Cohort 2, then a cohort will be added which will receive a loading dose of 320 mg and a maintenance dose of 40 mg.

\*2: If a cohort is added, and the additional cohort continues to the end and no problems with tolerability are found, then the study will proceed to Part B.

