## **7.6 Procedures for Discontinuation or Withdrawal of a Subject**

If a subject meets the criteria described in Section 7.5, the investigator will withdraw the subject from the study. Furthermore, subjects may withdraw from the study without providing a reason at any time during the study. If a subject withdraws from the study, the investigator will enter the primary reason for withdrawal in the eCRF, and will perform all procedures scheduled for the Early Termination Visit.

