#### 8.1.3.2 Criteria for Dose Holds and Dose Reduction

Part A: If a treatment-related AE occurs, or if it would be difficult to continue with TAK-385 treatment, then the dose of TAK-385 will not be reduced, and study treatment will be interrupted if necessary.

Part B: If a treatment-related AE occurs or if it would be difficult to continue with TAK-385 treatment, then study treatment will be interrupted if necessary. Subjects who experience serious AEs requiring study treatment interruption within 12 weeks (84 days) following treatment initiation may have their doses reduced by one dose level – 40 mg – following a 2-week treatment interruption period. If the AE continues even after dose reduction, or the subject's serum testosterone level exceeds 50 ng/dL for 4 to 6 weeks following dose reduction, then TAK-385 treatment will be discontinued so that the subject may receive some other therapy. If a serious AE requiring study treatment interruption occurs on or after Week 13 (Day 85) following treatment initiation, and the subject's treatment has not been interrupted prior to that, then the subject's treatment may be interrupted for 2 weeks and then resumed. However, if the AE recurs following study treatment resumption, or if the AE does not resolve even after 2 weeks of treatment interruption, then the subject will be withdrawn from the study.

Even if the dose has been increased in accordance with Section 8.1.3.1, when reducing the dose, it will be reduced by one dose level. Dose reduction will not be performed for subjects in the 40 mg group. In addition, if the dose is reduced in accordance with this section, then the dose may not be increased as described in Section 8.1.3.1.

Furthermore, if a LFT abnormality is found, it will be handled as shown in [Table 8.c](#).

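### For an early Part B serious AE still unresolved after the 2-week hold, Protocol 8.1.3.2 appears to permit restart at a lower dose, whereas 7.5 and 7.6 require withdrawal

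*Protocol*

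**What the plan says.** Protocol 7.5, item 1, gives as a reason for withdrawal a serious AE for which drug is temporarily stopped and "the AE recurs following study treatment resumption, or does not resolve event after 2 weeks of treatment interruption". The clause carries no limit by Part or by day of onset. The next clause, on DLTs, is confined to Part A, so the drafters did limit by Part where they meant to. Section 7.6 makes the consequence mandatory: "If a subject meets the criteria described in Section 7.5, the investigator will withdraw the subject from the study". Section 6.1 says for Part B that "study drug will be administered until the discontinuation criteria (Section 7.5) are met for each individual subject".

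Section 8.1.3.2 sets out two paths for Part B.

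- **Early path.** Subjects with serious AEs "requiring study treatment interruption within 12 weeks (84 days) following treatment initiation may have their doses reduced by one dose level", that is by 40 mg, once a 2-week interruption is over. Resolution of the AE is not a condition. The path has its own stop rule: "If the AE continues even after dose reduction", or if testosterone stays above 50 ng/dL for 4 to 6 weeks, TAK-385 is discontinued.
- **Later path.** "If a serious AE requiring study treatment interruption occurs on or after Week 13 (Day 85"), and treatment has not been interrupted before, drug may be held for 2 weeks and resumed. The sentence that follows reads "However, if the AE recurs following study treatment resumption, or if the AE does not resolve even after 2 weeks of treatment interruption", and its outcome is withdrawal.

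The section also states: "Dose reduction will not be performed for subjects in the 40 mg group". The early path therefore concerns only the 80 mg and 120 mg groups.

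**The concern.** For one clinical situation, the dosing section and the discontinuation section appear to call for different actions. A site that works from 8.1.3.2 alone could give drug again to a man whose serious AE has not resolved, in a part of the study whose primary objective is safety. In the 80 mg group, restart would be at 40 mg, a dose that Protocol 4.1.2.5 reports did not maintain castration levels between Days 14 and 28 in healthy men. The benefit to set against the risk is therefore doubtful.

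Reporting could also become inconsistent. SAP 2.3.1 counts dose reductions for AEs, and SAP 2.3.2 lists 80 / 40 mg and 120 / 80 mg among its example dosing patterns. SAP 2.1.6.1 has a deviation category for breaches of the discontinuation criteria. A single restart could be counted both as an ordinary dose reduction and as a deviation, although the dosing section appears to allow it.

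**Working it through.** No figure in the plan is at issue. The check sets the sections side by side for one subject and then bounds how many subjects and how much time it can concern.

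**The case.** A Part B subject in the 80 mg or 120 mg group has a serious AE, drug is held for 14 days, and the AE has not resolved.

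| | Hold from Day 84 (last early day) | Hold from Day 85 (first later day) |
|---|---|---|
| End of 2-week hold | 84 + 14 = Day 98 | 85 + 14 = Day 99 |
| 7.5 item 1 with 7.6 | Withdraw | Withdraw |
| 8.1.3.2 | Reduction by 40 mg may follow; no resolution condition | Withdraw |
| Sections agree? | Not on the face of 8.1.3.2 | Yes |

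The apparent restart doses are 80 − 40 = 40 mg and 120 − 40 = 80 mg. If the dose has been increased, the reduction is still one level: 120 − 40 = 80 mg and 160 − 40 = 120 mg.

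**Does the withdrawal sentence in 8.1.3.2 reach the early path?** It opens with *However*, directly follows the Day 85 rule, and picks up that rule's idea of resuming treatment. The early path already has a stop rule of its own. If every AE unresolved at 2 weeks led to withdrawal, the words "If the AE continues even after dose reduction" would have almost nothing left to do. The more natural reading is one stop rule for each path.

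**Which section controls?** In 8.1.3.2 the reduction is optional (*may*). In 7.6 withdrawal is required (*will*). Section 6.1 ends Part B dosing when a 7.5 criterion is met. An investigator who withdraws the subject complies with all four sections; one who restarts breaches 7.5 item 1 and 7.6. Withdrawal is therefore the controlling outcome, and 8.1.3.2 is the section out of line.

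**Bounds.**

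- Subjects: 2 groups × 15 = 30, or 15 if a 40 mg group replaces the 120 mg group.
- Time: 48 weeks × 7 = 336 days; 84 / 336 = 25% of the main treatment period. This is a share of calendar time, not of risk.
- Event rate: none is given for this population, so none is computed. In the overseas study described in 4.1.2.5, no SAE occurred among 128 healthy men given TAK-385 for at most 28 days. That suggests the case is uncommon, but the men were healthy and exposure was short.

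**The case against.** The strongest reply is that there is no true conflict: an optional dose reduction sits inside a mandatory stop rule, and 6.1 states that order for Part B. This stands as far as the outcome goes. A reader might infer that the protocol directs sites to restart men with unresolved serious AEs, or that the sections cannot be reconciled. The documents do not support either inference. What remains is that 8.1.3.2, where a site would look for the dosing decision, neither states the condition nor refers to 7.5 for this case.

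A second reply is that the withdrawal sentence in 8.1.3.2 nearly repeats 7.5 item 1, which has no time limit and also speaks of resumption. Both may state one general rule covering both windows. This reading is possible and would remove the problem. It is weaker because it leaves the early path's stop rule almost idle. The inference from *continues* is not conclusive, however. Section 10.1.11 lets an AE that apparently resolves and returns count as one intermittent event, and the English text appears to be a translation, so fine parsing has limits.

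Third, the harm requires a site to read 8.1.3.2 in isolation. SAEs reach the sponsor within 24 hours (10.2.2), well before a restart that follows a 2-week hold, and drug is stopped again if the AE continues after reduction. This stands and keeps the point minor.

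A reader might also infer that Table 8.c, which holds drug until liver tests are stable, needs an exemption from the 2-week limit. The documents do not support treating that as a consistency edit. The limit in 7.5 applies to serious AEs, and categories C and D require total bilirubin below 1.5 × ULN. Under the liver-specific rule in 10.1.5.1, such an elevation could be serious only through PT-INR above 1.5, and 7.5 already stops drug at once for that. An exemption would matter only for an event serious on other grounds, and there it would loosen an existing safety limit.

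**Conclusion.** The point holds as a minor inconsistency. For a Part B serious AE requiring interruption in the first 84 days and unresolved after the 2-week hold, 8.1.3.2 appears to permit restart 40 mg lower. Sections 7.5 and 7.6, with 6.1, require withdrawal and control when the sections are read together. The dosing section should be brought into line with them.

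The conclusion rests on reading the withdrawal sentence in 8.1.3.2 as belonging to the Day 85 path; confidence in that reading is medium. The 84 days may be timed from the AE or from the interruption. That choice could decide which path applies near the boundary, but it does not remove the inconsistency.

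**What to change.** Two edits to the Part B early path of 8.1.3.2:

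1. Add: *Dose reduction and restart are subject to Section 7.5: a subject whose serious AE has not resolved after the 2-week interruption will be withdrawn.*
2. Reword the stop rule so that it applies when the AE *continues or recurs after dose reduction*. This matches the recurrence limb of 7.5 item 1 and covers intermittent events.

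Table 8.c should be left as it is. How to handle a category C or D elevation that is serious on other grounds is a separate policy question for the sponsor.

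The cost is one new sentence and one reworded clause in the next amendment, with no added visits, tests or subjects.

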**Table 8.c Guidelines for Handling Liver Function Test Abnormalities**

Category	ALT, AST, and Total Bilirubin	Study Drug	ALT and AST Tests	Treatment Interruption	Dose Adjustment
A	ALT or AST $\geq 1.5 \times$ ULN to $< 3 \times$ ULN AND Total bilirubin $< 1.5 \times$ ULN	Continue without changing the dose	Perform tests every week for 2 weeks, and then every 2 weeks for 4 weeks until stable *1	Not necessary	Not necessary
B	ALT or AST $\geq 3 \times$ ULN to $< 5 \times$ ULN AND Total bilirubin $< 1.5 \times$ ULN	Continue without changing the dose	Perform tests every week, and then every 2 weeks for 4 weeks until stable *1	Not necessary	Not necessary
C	ALT or AST $\geq 5 \times$ ULN to $< 8 \times$ ULN AND Total bilirubin $< 1.5 \times$ ULN	Interrupt treatment	Perform 2 tests in the first week, then every week for 2 weeks, and then every 2 weeks until stable *1	Interrupt treatment until stable *1	Reduce the TAK-385 dose to 40 mg
D	ALT or AST $\geq 8 \times$ ULN to $< 20 \times$ ULN AND Total bilirubin $< 1.5 \times$ ULN	Interrupt treatment	Perform 2 tests a week for the first 2 weeks, and then every 2 weeks until stable *1	Interrupt treatment until stable *1	Reduce the TAK-385 dose to 40 mg *2
E	ALT or AST $\geq 3 \times$ ULN AND Total bilirubin $> 2 \times$ ULN (Hy's law)	Permanently discontinue treatment	Perform 2 tests a week until the test values drop, and then every week until stable *1	N/A	N/A

\*1: Stable means ALT and AST both CTCAE Grade 1 ( $> ULN$  to  $3 \times ULN$ )

\*2: The study sponsor should be consulted before resuming treatment.

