**Table 9.a Clinical Laboratory Tests**

Hematology	Chemistry	Metabolic Panel	Urinalysis
RBC	Total protein	Triglycerides	pH
WBC	Albumin	Total cholesterol	Specific gravity
Hemoglobin	Glucose	HDL cholesterol	Protein (qualitative)
Hematocrit	Creatinine	LDL cholesterol	Glucose (qualitative)
Platelet count	BUN	TSH	Occult blood (qualitative)
Differential WBC (neutrophils [including absolute count], basophils, eosinophils, lymphocytes, monocytes)	Uric acid	HbA1c	Ketones (qualitative)
	Total bilirubin		Urobilinogen (qualitative)
	ALT		Bilirubin (qualitative)
	AST		
	LDH		
	γ-GTP		
	ALP		
	CK(CPK)		
	Na		
	K		
	Cl		
	Ca		
	P		
	PT-INR		

Tests to be conducted when determining eligibility

(to be performed only when deemed necessary)

HIV test; hepatitis tests including HBsAg and anti-HCV; serologic test for syphilis

---

The above clinical laboratory tests will be performed at the medical institution. The investigator will evaluate and archive reported clinical laboratory test findings.

When the ALT or AST levels are  $> 3 \times \text{ULN}$ , retesting (at least ALP, ALT, AST, total bilirubin,  $\gamma$ -GTP, and PT-INR) will be performed within 48 to 72 hours (within 7 days at the latest).

(See Section 7.5 for the criteria for the withdrawal from the study. See Section 10.2.3 for the reporting of LFT abnormalities in cases where the ALT or AST level exceeds  $3 \times \text{ULN}$ , and the total bilirubin level exceeds  $2 \times \text{ULN}$  or the PT-INR exceeds 1.5.)

The investigator will archive the reference ranges for the clinical laboratory tests, including the history.

All clinically relevant, abnormal laboratory test values will be input in the source data and eCRF of the subject as AEs, etc. All clinically relevant, abnormal laboratory test values verified by retesting will be followed up in all subjects until the abnormal value returns to an acceptable level or there is a sufficient explanation for the observed change.

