#### 10.1.5.1 Liver Function Test Abnormalities

LFT abnormalities were identified as specific AEs because nonclinical studies in monkeys revealed LFT abnormalities and because clinical studies on oral GnRH antagonists with the same backbone structure as TAK-385 have revealed elevated AST and ALT as common treatment-related AEs.

The management of LFT abnormality AEs is presented in Table 8.c of the protocol. When ALT or AST levels are  $> 3 \times$  ULN, retesting will be performed within 48 to 72 hours (within 7 days at the latest). As soon as they become aware that ALT or AST levels are  $> 3 \times$  ULN, investigators will discuss detailed information on affected subjects and other potential causes with the sponsor to review whether the administration of study drug should be discontinued immediately.

If ALT or AST levels are  $> 3 \times$  ULN and total bilirubin levels are  $> 2 \times$  ULN or the PT-INR is  $> 1.5$ , and investigators conclude that the levels cannot be explained by any factor other than study drug based on the results of retesting, then they will be handled as serious AEs.

When LFT abnormalities correspond to the criteria in Section 7.5, investigators will immediately discontinue administration of study drug and will perform appropriate follow-up.

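### The liver dosing table (Table 8.c) omits the PT-INR arm of the Section 7.5 stop rule, so rows B to D contradict it when PT-INR exceeds 1.5 and bilirubin is below 1.5 × ULN

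*Protocol*

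**What the plan says.** Section 7.5, under adverse events as a reason for discontinuation, gives one liver criterion: "ALT or AST > 3 × ULN; AND total bilirubin > 2 × ULN or PT-INR > 1.5". When it is met, "study drug administration will be discontinued immediately". Section 7.6 adds: "If a subject meets the criteria described in Section 7.5, the investigator will withdraw the subject from the study".

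The dosing instruction sits elsewhere. The last sentence of Section 8.1.3.2 says that "if a LFT abnormality is found, it will be handled as shown in" Table 8.c, with no exception. The table defines its five rows by ALT, AST and total bilirubin:

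- Row B, ALT or AST from 3 to below 5 × ULN with bilirubin below 1.5 × ULN: "Continue without changing the dose".
- Rows C and D, 5 to below 8 and 8 to below 20 × ULN with the same bilirubin limit: interrupt until stable, then "Reduce the TAK-385 dose to 40 mg". Row D has a footnote requiring sponsor consultation before treatment resumes.
- Row E, ALT or AST at or above 3 × ULN with bilirubin above 2 × ULN: permanent discontinuation.

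Section 10.1.5.1 names Table 8.c as the management scheme for liver-test events, and then closes with: "When LFT abnormalities correspond to the criteria in Section 7.5, investigators will immediately discontinue administration of study drug".

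**The concern.** Row E, the only permanent-stop row, reproduces the bilirubin half of the 7.5 rule and leaves out the PT-INR half. A subject with raised transaminases, near-normal bilirubin and PT-INR above 1.5 meets the stop rule but falls in a row that says something else. In row B the stated action is the opposite one: full-dose treatment goes on.

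Liver-test abnormality is the only special-interest adverse event the protocol names. Section 10.1.5.1 treats this same laboratory combination as a serious adverse event if retesting leaves the drug as the only explanation.

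The combination can occur. PT-INR is in the routine chemistry panel (Table 9.a). The exclusion criteria set no PT-INR limit, and exclusion 12c allows stable anticoagulant therapy for atrial fibrillation. Whether such therapy would raise PT-INR in a given subject is an assumption, because the protocol names no agent.

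**Working it through.** The plan states no figure to reproduce here. The check is whether two written rules give the same action for the same laboratory result.

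**Rules as coded.** Let a be the higher of ALT and AST in multiples of ULN, b total bilirubin in multiples of ULN, and i PT-INR.

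- Section 7.5: stop if a > 3 and (b > 2 or i > 1.5). Sections 9.1.8 and 10.1.5.1 group the terms the same way.
- Table 8.c: row A if 1.5 ≤ a < 3 and b < 1.5; row B if 3 ≤ a < 5 and b < 1.5; row C if 5 ≤ a < 8 and b < 1.5; row D if 8 ≤ a < 20 and b < 1.5; row E if a ≥ 3 and b > 2. PT-INR appears in no row.

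**Results at b = 1.0 and i = 1.6:**

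| ALT or AST (× ULN) | Table 8.c | Section 7.5 | Agree? |
|---|---|---|---|
| 2 | A: continue | not met | yes |
| 3.0 | B: continue | not met (rule is > 3) | yes |
| 3.5, 4.9 | B: continue | stop | no |
| 5, 7.9 | C: interrupt, then 40 mg | stop | no |
| 8, 19.9 | D: interrupt, then 40 mg after sponsor consultation | stop | no |

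All six points above 3 × ULN that fall in rows B to D conflict, so 3 of the 5 rows are affected. With PT-INR at 1.0, no point from 2 to 25 × ULN conflicts. With bilirubin at 2.5 × ULN, every point above 3 × ULN lands in row E and agrees with 7.5. The conflict therefore comes entirely from the missing PT-INR arm.

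**The kind of conflict differs by row.** Row B differs on the immediate action. Rows C and D already halt dosing at once, and differ only on whether dosing may resume. Section 8.1.3.2 bars dose reduction in Part A, so the 40 mg step is in practice a Part B matter.

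**Where the threshold appears.** The PT-INR > 1.5 limit is written in six places: Sections 6.1.2.1, 7.5, 9.1.8, 10.1.5.1, 10.2.1.3 and 10.2.3. It is absent from Section 8.1.3.2 and Table 8.c, which set the dose.

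**Cases with no row.** Some results with PT-INR above 1.5 meet 7.5 but fit no row of the table: bilirubin from 1.5 to 2 × ULN with ALT or AST above 3 × ULN, and ALT or AST at 20 × ULN or more with bilirubin not above 2 × ULN. There the table is silent and does not contradict 7.5.

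**The case against.** The strongest reply is that the protocol already says which rule wins. Section 10.1.5.1 refers to Table 8.c and then requires immediate discontinuation when 7.5 is met, and Section 7.6 makes withdrawal mandatory. Row B is also never the only instruction above 3 × ULN. As soon as an investigator knows of such a value, 10.1.5.1 requires a discussion with the sponsor on whether to stop immediately. Section 9.1.8 requires a retest that includes PT-INR and points to 7.5, and Section 10.2.1.3 sets a 24-hour report. In Part A, Section 6.1.2.1 makes a treatment-related, confirmed abnormality of this kind a dose-limiting toxicity, which is itself a reason to discontinue. The table is titled as guidelines, and a reader who applies every section will stop the drug.

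Most of this stands, and it limits the practical risk. It rules out two stronger readings. A reader might infer that the protocol leaves open which rule governs; Sections 7.6 and 10.1.5.1 settle that in favour of 7.5. A reader might also count the doses taken under row B before the 24-hour report or the retest. The documents do not support such a count, because the sponsor review comes first and has no fixed delay, and neither the report nor the retest is a stopping rule.

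The defect in the table remains. The override is in the adverse-event chapter, while the dosing section sends all liver-test abnormalities to a table that lacks the trigger and does not mention 7.5. Row B's own follow-up column asks for ALT and AST only. The argument that the table concerns only holds and reductions is weakened by row E, which is itself a permanent stop.

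**Conclusion.** The point holds as an internal contradiction that should be corrected. With bilirubin below 1.5 × ULN and PT-INR above 1.5, row B directs continued dosing where 7.5 requires an immediate stop. Rows C and D permit resumption at 40 mg where 7.5 and 7.6 require withdrawal. Three of five rows are affected, one of them on the immediate action.

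This rests on the wording of the current protocol alone. The documents give no frequency for this laboratory combination, so no number of patients or extra doses is claimed. Because other sections make 7.5 govern and require prompt sponsor review, the finding is that the dosing table misstates the governing rule, and not that subjects would be left on drug.

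**What to change.** Make three changes in one amendment:

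1. State in Section 8.1.3.2, and in a footnote to Table 8.c, that Section 7.5 takes precedence over the table.
2. Keep row E's bilirubin arm and add a second arm: or ALT or AST > 3 × ULN AND PT-INR > 1.5. Use > 3 and not ≥ 3 in the new arm; otherwise row E would stop the drug at exactly 3.0 × ULN, where 7.5 does not.
3. Exclude from rows B to D any case with ALT or AST > 3 × ULN and PT-INR > 1.5.

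This removes every conflict. Any case meeting 7.5 has ALT or AST above 3 × ULN and either bilirubin above 2 × ULN or PT-INR above 1.5, so it enters row E by one arm or the other. Rows B to D cannot hold it, because they already require bilirubin below 1.5 × ULN and would now exclude the PT-INR cases. The new arm also covers the PT-INR cases that have no row today.

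The cost is a table edit, a footnote and one sentence. ALT, AST, bilirubin and PT-INR are already in the same chemistry panel, so no test or visit is added.
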